There are transgender females who report an anecdotal improved breast development, mood, or sleep with the use of progestogens(7). Estrogen is important for stromal and early ductal and epithelial proliferation(2). By contrast, although progesterone in cell culture causes proliferation for a few days, it then transforms into its primary, maturational role that includes inhibition of the proliferative effects of E2 (7, 8). Progesterone appears to be relevant for acini/lobuli development and pseudolactational changes. Many women report a feeling of fullness in breasts and their transformation from a conical to more rounded shape (clinical experience of PI). Thus, progesterone may induce optimal breast maturation, if preceded by estradiol therapy in transwomen. However, observational studies with small number of patients do not support a major role for progesterone in enhancing breast size in transwomen (9). There have been no well-designed studies of the role of progestogens in feminizing hormone regimens, so the question is still open. As per Endocrine society transgender guidelines, “current evidence does not indicate that progestogens enhance breast development in transgender females, nor does evidence prove the absence of such an effect. This prevents us from drawing any firm conclusion at this moment and demonstrates the need for further research” (1).

Progesterone has a minor suppressive effect on GnRH production, and this would decrease endogenous testosterone production. In a chart review, transwomen using medroxyprogesterone (in combination with estradiol and spironolactone) had lower testosterone concentrations than those on estradiol and spironolactone alone (79 vs 215 ng/dl)(10). Progesterone also competes for the 5- $\alpha$  reductase enzyme that converts T into dihydrotestosterone (11). These effects would theoretically be desirable in the feminization of transwomen.

We plan to conduct a randomized, placebo controlled double blind study evaluating the effect of adding progesterone for 6 months to transwomen who are being treated with estradiol. We hypothesize

that progesterone will decrease serum testosterone concentrations as compared to placebo and increase breast size. We will also assess its role in mood, sleep, scalp hair and androgenic hair growth.

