2. HIV
3. Planning to go for breast enhancement or gender reassignment surgery in the next 6 months
4. Known history of peanut allergy (because the study drug contains peanut oil)
5. Active deep vein thrombosis, pulmonary embolism or history of these conditions
6. Active arterial thromboembolic disease or history of these conditions
7. Active cardiovascular disorders or history of these conditions (e.g. myocardial infarction, uncontrolled hypertension >150/90 mmHg)
8. Known, suspected, or history of breast cancer
9. Known liver dysfunction or disease
10. Known or history of gallbladder disease. This does not apply to subjects who have undergone cholecystectomy
11. Known or history of hypertriglyceridemia (>400 mg/dl)

**Screening visit:** Informed consent will be obtained. This visit may be conducted during the PI's clinic (if the study volunteer is PI's patient) or at Endocrinology clinical research space at Salus Center. Vital signs (blood pressure, heart rate and weight) will be measured and a general physical examination will be performed.

Subjects who qualify and consent to take part in the study will be assigned a number by a computerized random number generation program and will be randomized (1:1) to receive either progesterone or placebo. An unblinded pharmacist will prepare the study product. Study investigators, staff and the study participants will be blinded.

**Week 0 (baseline):** Subjects will come fasting to the Salus Center. Breast exam and testicular exam will be conducted. They will complete the study questionnaires. Blood sample will be taken for total testosterone, total estradiol, sex hormone binding globulin (SHBG), LH, FSH, complete blood count (CBC), comprehensive metabolic panel (CMP) and research labs. For subjects who are on intramuscular estradiol, this visit will be performed 3-4 days after their last injection. Subjects will be randomized to receive generic micronized progesterone 200 mg or placebo tablets, to be taken at bedtime daily. They will be given a 3-month supply of the study drug. Subjects will be asked to bring the pill bottles back with them at the next visit to assess compliance.

**Week 4:** Subjects will be called by the study coordinator to counsel on drug compliance and to ask for side-effects.

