**Week 12:** Subjects will come fasting to the Salus Center. For subjects who are on intramuscular estradiol, this visit will be performed 3-4 days after their last injection. Vital signs (blood pressure, heart rate and weight) will be measured and a general physical examination will be performed. Blood sample will be taken to measure total testosterone, total estradiol, SHBG, LH, FSH and research labs. They will complete the study questionnaires. They will be given a 3-month supply of the study drug. Subjects will be asked to bring the pill bottles back with them at the next visit.

**Week 24 (end of study):** Subjects will come fasting to the Salus Center. For subjects who are on intramuscular estradiol, this visit will be performed 3-4 days after their last injection. Blood sample will be taken to measure CBC, CMP, total testosterone, total estradiol, SHBG, LH, FSH and research labs. Vital signs (blood pressure, heart rate and weight) will be measured and a general physical examination will be performed. Breast exam and testicular exam will be conducted. They will complete the study questionnaires. They will then be discharged from the study.

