- b) Symptom-Checklist-K-9 (SCL-K-9) to measure psychological distress level(20): This questionnaire has 9 questions and is meant to assess overall psychological distress. Responses are recorded on a 5 point Likert scale. The mean of all 9 questions is presented as the global severity index.

*Sleep quality:* We will use single-item sleep quality scale (SQS) to assess change in sleep quality during the study.

FG score calculator and study questionnaires are attached in the IRB application.

*Research labs:* 10 ml of blood will be obtained for research. Serum will be stored for future analysis based on study results. For example, if there is a decrease in FG score, we will check dihydrotestosterone levels.

**Side effects:** Progesterone may cause fluid retention, mood swings, breast tenderness, depression, transient dizziness and drowsiness, headache, abdominal pain or bloating, hot flashes in women. Long term use is associated with possibly increased risk of heart disease and stroke in women after menopause. Short term and long term risks in transwomen are not known.

If a significant or serious adverse event occurs, the subject will cease participation in the study. Discovery of two or more patients experiencing a significant or serious adverse event will lead to stopping of this study altogether.

**Statistical analysis:** The primary end-point of the study is change in total testosterone concentrations in transwomen after progesterone treatment at 24 weeks as compared to placebo. Transformations of the

data to meet statistical assumptions may be considered. *t*-test will be used for comparison. We estimate that testosterone concentrations will decrease by 20%. A sample size of 20 subjects per group (assuming a drop-out rate of 15%) will provide adequate power ( $\beta = 0.8$ ) to detect a significant difference ( $\alpha = 0.05$ ), provided the pooled standard deviation is not greater than the mean difference. Hence, we will recruit 40 transwomen in this study.

*Secondary end-points:* Change at weeks 12 and 24 in a) LH and FSH concentrations, b) breast size, breast hemi-circumference, areolar diameter, Tanner stage, feeling of fullness in breast, bra cup size, c) FG score, shaving frequency, scalp hair growth, scalp hair quality, d) global severity index scores on BUT-BIC and SCL-K-9 scales, e) SQS score.

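### The primary t-test on 24-week change in testosterone fixes the baseline slope at 1; a prespecified ANCOVA would estimate it, at a cost of about one point of power at most and a gain of unknown size

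*Combined protocol and SAP*

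**What the plan says.** The Statistical analysis paragraph defines the endpoint: "The primary end-point of the study is change in total testosterone concentrations in transwomen after progesterone treatment at 24 weeks as compared to placebo". On method, it says of transformations of the "data to meet statistical assumptions may be considered. *t*-test will be used for comparison". It names no covariate, and it gives no rule or date for choosing the scale.

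The sample-size sentence reads "A sample size of 20 subjects per group (assuming a drop-out rate of 15%) will provide adequate power" at alpha 0.05, "provided the pooled standard deviation is not greater than the mean difference". The expected effect is a 20% decrease. The paragraph does not say whether the SD is that of change or of single values, or on which scale.

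Total testosterone is in the planned blood draw at all three visits:
- Week 0: "Blood sample will be taken for total testosterone, total estradiol, sex hormone binding globulin (SHBG), LH, FSH"
- Week 12: "Blood sample will be taken to measure total testosterone, total estradiol, SHBG, LH, FSH and research labs"
- Week 24: "Blood sample will be taken to measure CBC, CMP, total testosterone, total estradiol, SHBG, LH, FSH and research labs"

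**The concern.** A change score subtracts the whole baseline value, which amounts to assuming that week-24 testosterone tracks baseline with a slope of exactly 1. If the true slope is lower, the subtraction adds noise, and chance differences between the arms at baseline are over-corrected. ANCOVA estimates the slope from data the trial collects anyway.

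This matters because the sample size is the smallest that reaches 80% power, and it rests on an SD condition that the documents do not support with data. The background gives testosterone figures from a chart review, where users of medroxyprogesterone "had lower testosterone concentrations than those on estradiol and spironolactone alone (79 vs 215 ng/dl"), but no SD. Any precision available from baseline would widen that margin.

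**Working it through.** **Inputs from the plan.** 20 per arm, 15% drop-out, alpha 0.05 (taken as two-sided), power 0.80, SD equal to the mean difference (standardised effect 1), 20% fall. **Assumed.** The SD is read as the SD of change. The baseline-to-week-24 correlation ρ is not in the documents, so a range is shown.

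**1. The plan's own figure.** Completers per arm: 20 × 0.85 = 17. Noncentrality is 1/√(2/17) = 2.915 on 32 df, critical value 2.037, power 80.7%. With 16 per arm power is 78.1%, so 17 is the minimum, and 17/0.85 = 20. The stated sample size reproduces. Power stays at 80% only while SD/difference is at most 1.009.

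**2. Equal SDs at the two visits.** With common SD σ, the change score has variance 2σ²(1 − ρ) and the ANCOVA residual has variance σ²(1 − ρ²). Their ratio is (1 + ρ)/2. ANCOVA power comes from the noncentral t on 34 − 3 = 31 df, averaged over chance baseline imbalance. The last column is the between-person CV implied when the SD of change equals the 20% fall: CV = 0.2/√(2(1 − ρ)).

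| ρ (assumed) | Variance ratio | ANCOVA power | Largest SD/difference for 80% | Completers per arm for 80% | Implied CV |
|---|---|---|---|---|---|
| 0.3 | 0.65 | 93% | 1.230 | 12 | 17% |
| 0.5 | 0.75 | 89% | 1.145 | 14 | 20% |
| 0.7 | 0.85 | 85% | 1.076 | 15 | 26% |
| 0.9 | 0.95 | 81% | 1.018 | 17 | 45% |
| t-test on change | 1 | 80.7% | 1.009 | 17 | – |

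Break-even is at ρ = 0.932, where the implied CV is about 54%. At ρ = 0.95 ANCOVA power is 80.4%, a loss of about 0.4 point. With all 40 evaluable, break-even is 0.943.

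**3. Unequal SDs.** Let k be the week-24 SD divided by the baseline SD. In units of baseline variance, the change score has variance 1 + k² − 2ρk and the ANCOVA residual k²(1 − ρ²). The difference is (1 − ρk)², which is never negative. ANCOVA can therefore lose only the cost of estimating the slope. That cost is greatest when ρk = 1, where power is 79.4%, a loss of 80.7 − 79.4 = 1.3 points.
- k = 0.8 or 0.9: ANCOVA wins at every correlation tried.
- k = 1.1: slightly worse for ρ of about 0.80 to 0.96.
- k = 1.2: slightly worse for ρ of about 0.70 to 0.91.

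**4. Skewed baselines.** Simulation with 17 per arm, 60,000 replicates, and assumed between-person log-SDs of 0.2, 0.5 and 0.83. Each entry is t-test power, then ANCOVA power.

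| Model and scale | 0.2 | 0.5 | 0.83 |
|---|---|---|---|
| Proportional 20% fall, raw | 0.737, 0.856 | 0.640, 0.721 | 0.492, 0.582 |
| Proportional 20% fall, log | 0.808, 0.871 | 0.806, 0.810 | 0.808, 0.801 |
| Additive fall, raw | 0.808, 0.863 | 0.805, 0.807 | 0.785, 0.780 |
| Additive fall, log | 0.821, 0.844 | 0.676, 0.664 | 0.560, 0.555 |

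The worst loss from adjusting is 0.676 − 0.664, or 1.2 points. With no treatment effect, ANCOVA rejected in 4.2 to 5.0% of replicates.

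**The case against.** The strongest reply is that the plan has done nothing wrong. The t-test is valid under randomisation and delivers the power claimed. Having little slack is what any sample size set at the minimum looks like. That stands, and it is why this is a suggestion.

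The second reply is that the large gains need a narrow spread of testosterone. Under the plan's 20% fall with a matching SD of change, the 93% and 89% figures require a between-person CV of about 20% or less. In the wider-spread simulations, on the scale that fits the model, adjusting moved power by between about −1 and +0.4 points. That also stands. The documents give no CV, so the actual gain is unknown.

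Four stronger readings are tempting, and the documents do not support them:
- **That the test ignores baseline.** Change subtracts it. The Study endpoints list says only serum testosterone concentrations, but the Statistical analysis paragraph defines the endpoint as change.
- **That 0.93 is a general threshold.** It assumes equal SDs, normal data and 34 completers. In the additive log-scale cases, ANCOVA lost slightly at correlations of about 0.8.
- **That the open choice of scale inflates the error rate.** Transformation is tied to statistical assumptions, and the Screening visit section blinds investigators and staff.
- **That logs are the better scale because the effect is stated as a percentage.** Log ANCOVA beats raw ANCOVA by 1, 9 and 22 points under the proportional model. Under the additive model it falls 14 and 23 points below the raw change t-test at log-SD 0.5 and 0.83.

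**Conclusion.** The point holds as a low-cost improvement, not as a fault. The primary analysis fixes the baseline slope at 1 when the data to estimate it are already planned. What is firm is the asymmetry: in the cases computed, adjustment costs at most about 1.3 points of power, and it gains about 9 points at a correlation of 0.5 and 5 at 0.7. Those gains assume equal SDs, 17 completers per arm and an SD of change equal to the difference.

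What is not firm is where this trial sits. The correlation, the spread of testosterone and the ratio of the two SDs are all absent from the documents. If testosterone varies widely between participants, the benefit on the appropriate scale may be close to nil. Adjustment also does not rescue the unsupported SD condition: at a correlation of 0.9 the tolerable ratio rises only from 1.01 to 1.02.

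**What to change.** Amend the Statistical analysis paragraph so that:
- the primary analysis is an ANCOVA of week-24 total testosterone on arm, with baseline total testosterone as covariate and both on the same scale;
- that scale is fixed once, before unblinding, from prior clinic data or from pooled blinded week-0 and week-12 values, by checking whether the spread of within-person change grows with the level;
- the effect measure follows the scale: a difference in means on the raw scale, a ratio of geometric means on the log scale;
- the SD condition in the sample-size sentence is restated on that scale, as the SD of change;
- the unadjusted t-test on change is kept as a sensitivity analysis.

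The cost is wording, with no new visit, sample or assay. Statistically, it is one degree of freedom and at most about 1.3 points of power in the cases computed. If the log scale is chosen, add one rule for values below the assay limit; these are plausible because participants have had at least 6 months of estradiol.

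### The primary t-test on week-24 change leaves baseline (as a covariate) and week-12 testosterone unused: an inefficiency and a risk of bias, although planned power is met at 15% random drop-out

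*Combined protocol and SAP*

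**What the plan says.** All references are to the combined protocol and SAP.

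- **Primary endpoint (Statistical analysis).** It is "change in total testosterone concentrations in transwomen after progesterone treatment at 24 weeks as compared to placebo".
- **Method (same section).** The only method named is a t-"test will be used for comparison". Data transformation is left open. No covariate, analysis set, missing-data rule or sensitivity analysis is given.
- **Sample size (same section).** 20 per arm, 40 in all, "assuming a drop-out rate of 15" per cent, for power 0.8 at alpha 0.05, on condition that the pooled SD is no larger than the mean difference.
- **Week 12.** "Blood sample will be taken to measure total testosterone, total estradiol, SHBG, LH, FSH and research labs". Baseline (Week 0) and Week 24 also include total testosterone, and one assay method is specified for it (Clinical laboratory assays).
- **Secondary end-points.** Weeks 12 and 24 are named for LH, FSH, breast, hair, mood and sleep measures. Testosterone is not in that list, so its week-12 value enters no stated analysis.
- **Side effects.** "If a significant or serious adverse event occurs, the subject will cease participation in the study". The next sentence stops the whole study once two or more patients have had such an event.

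**The concern.** A two-sample t-test on week-24 change needs both a baseline and a week-24 value. Anyone without the latter drops out of the primary comparison, even if a week-12 testosterone value is on file. The sample size is built that way: the 3 expected losses per arm are counted as contributing nothing.

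Two things are at stake in a 40-person trial. The first is precision. Subtracting baseline is generally less efficient than adjusting for it as a covariate, and the week-12 values of people who later leave carry information about their week-24 values. The second is bias. If people leave because of how they are responding, and do so differently in the two arms, the completers no longer give a like-for-like comparison. Week 12 is the only post-baseline measurement of the primary variable that could correct for this.

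**Working it through.** **1. The plan's own figure.** Inputs from Statistical analysis: standardised difference 1 (SD equal to the mean difference), alpha 0.05 (sidedness not stated; two-sided reproduces the result), power 0.80, drop-out 15%.

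- The noncentral-t calculation gives n = 16.7, so 17 per arm; 17/(1 - 0.15) = 20.0. This matches the plan exactly.
- At 17 completers per arm: noncentrality √(17/2) = 2.92, 32 df, power 80.7%.
- With no losses, 20 per arm: √(20/2) = 3.16, 38 df, power 86.9%.

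The planned loss costs 86.9 - 80.7 = 6.2 points, and the recruitment target already pays for it.

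**2. Gain from baseline adjustment.** The documents give no correlations, so these are assumptions. With equal SD σ at each visit and baseline-to-week-24 correlation r:

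- SD of change = σ√(2(1 - r)); residual SD after adjustment = σ√(1 - r²).
- Their ratio is √(2/(1 + r)). At r = 0.6 it is √(2/1.6) = 1.118; at r = 0.9 it is √(2/1.9) = 1.026.

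A standardised difference of 1 on change therefore becomes 1.12 or 1.03. Simulated power at d = 1 on change, 20 per arm and 15% random loss after week 12:

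| Assumed correlations | t-test on change | Baseline-adjusted, completers | Repeated measures with week 12 |
|---|---|---|---|
| baseline-wk12 0.7, wk12-wk24 0.8, baseline-wk24 0.6 | about 0.80 | 0.87 | 0.89 |
| all 0.9 | 0.80 | 0.81 | 0.82 |

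The repeated-measures column assumes a week-12 effect of 80% of the week-24 effect. It was computed by its sequential-regression form: week 12 on baseline and arm in everyone with week 12, then week 24 on baseline, week 12 and arm in completers. In the first row baseline supplies about 7 of the 9 points and week 12 about 2.

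**3. Gain from week 12 alone, by formula.** Let m be the number of drop-outs per arm with a week-12 value, and r the correlation of week-12 with week-24 change. The variance is (1/17)(1 - r²m/(17 + m)) in units of SD².

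- r = 0.5, m = 1.5: 0.25 × 1.5/18.5 = 0.0203; effective n = 17/0.9797 = 17.4; power 81.5%.
- r = 0.9, m = 3: 0.81 × 3/20 = 0.1215; effective n = 17/0.8785 = 19.4; power 85.7%.

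That is about 1 to 5 points over 80.7%.

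**4. Bias when leaving depends on week-12 response.** True difference -1.00 SD, 15% loss overall. The mechanisms are assumed. Ranges span the strengths of dependence and correlations tried.

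| Who leaves | Completers' estimate | Estimate using week 12 |
|---|---|---|
| At random | -1.00 | -1.00 |
| One rule in both arms, by absolute week-12 fall (placebo loses 19-22%, progesterone 9-11%) | -0.96 to -0.88 | -0.99 to -1.00 |
| Poor responders relative to own arm, 15% in each | about -1.00 | about -1.00 |
| Poor responders in the progesterone arm only | -1.07 to -1.12 | about -1.00 |
| Opposite directions in the two arms | -1.13 to -1.24 | about -1.00 |

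Mid-strength versions of the second and fourth rows give about -0.94 and -1.08. The t-test's power is 0.74 to 0.78 in the second row, and about 0.88 in the fourth because the estimate is inflated. With no true effect and the second rule at its stronger setting, type I error stays near nominal: 0.049 for the t-test and 0.046 for the repeated-measures analysis.

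**The case against.** **The 15% is itself the allowance for drop-out.** A reader might infer that expected losses take power below 0.80. They do not: 17 completers give 80.7%. Power below 0.80 appears only under one assumed mechanism, by which placebo participants leave more often. This objection stands.

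**The direction of bias is not known.** A reader might infer that completers-only analysis pulls the estimate toward no effect. The documents say nothing about why people would leave, and other mechanisms exaggerate the effect or leave it unchanged. This also stands.

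**The documents give thin evidence for informative drop-out.** Withdrawal for a significant or serious adverse event is written in, but the study stops at two such patients, so that route cannot produce a 15% loss. Leaving for lack of benefit is conjecture: the trial is double-blind, and participants would notice breast, hair, mood or sleep changes rather than serum testosterone. If those drive leaving, a model of testosterone alone need not remove the bias. The clean correction in the last table arises because the simulated drop-out depends on the variable being modelled.

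**Discarding is inferred.** The plan never says that participants without week 24 are excluded. But a t-test on week-24 change, with no imputation rule, has no other way to treat them, and the sample size counts them as lost.

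**Week 12 adds little power.** This is true: most of the gain comes from baseline, and both gains shrink if correlations are high. Baseline-adjusted analysis of completers would be a defensible simpler choice on power grounds. It does not use the week-12 values of those who leave, so it does not address the bias.

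**Conclusion.** The point holds as an avoidable inefficiency and an unaddressed risk of bias. It is not an error in the sample size, and it does not show that the result would be biased in any given direction.

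The gain in power is about 9 points under the moderate assumed correlations and 1 to 2 points if all are 0.9. The possible bias is roughly 6 to 8% of the true effect either way at mid-strength dependence, more under stronger or opposing mechanisms, and nil when losses balance between arms. All of this rests on correlations and drop-out mechanisms that the documents do not give. A model using week 12 removes only the part of the bias explained by observed values.

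The case for changing the plan is that the data are already scheduled and the better method costs little. As written, the handling of missing week-24 values would have to be chosen after the plan, in a trial small enough for that choice to matter.

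**What to change.** Replace the primary t-test with a repeated-measures mixed model on log total testosterone at weeks 12 and 24. The log scale suits an effect stated as a 20% fall, and the plan already allows transformation.

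- **Terms:** arm, visit, arm-by-visit, baseline (log) and baseline-by-visit, with unstructured covariance and a small-sample degrees-of-freedom method such as Kenward-Roger. The simulations used the sequential-regression form, not this exact specification.
- **Analysis set:** all randomised participants with any post-baseline testosterone value, in the arm assigned.
- **Primary test:** the arm contrast at week 24, two-sided at 0.05.
- **Sensitivity analyses:** keep the t-test on week-24 change, and add one analysis that allows drop-out to depend on unobserved values, for example by shifting the assumed week-24 values of those who left over a stated range in each arm.
- **Reporting:** numbers and reasons for missing week-24 values by arm, and how many of those participants have a week-12 value.

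The cost is SAP wording and slightly more analysis work, with a result a little harder to explain than a t-test. No visits, samples or participants are added. The change does not recover anyone who leaves before giving a post-baseline value; they should be counted and covered by the sensitivity analysis.

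### Forty participants give about 81% power only for a standardised difference of 1.0; the plan gives no baseline mean, SD or source tying that to its 20% fall, and it labels power as beta

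*Combined protocol and SAP*

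**What the plan says.** All the relevant text is in the Statistical analysis paragraph at the end of Study Procedures.

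- The primary endpoint is "change in total testosterone concentrations in transwomen after progesterone treatment at 24 weeks as compared to placebo".
- The method is a *t*-test ("test will be used for comparison"), with no statement of one- or two-sided testing. The scale is left open: transformation of the "data to meet statistical assumptions may be considered".
- The expected effect is "We estimate that testosterone concentrations will decrease by 20" percent. No baseline mean and no expected placebo change accompany it.
- Twenty per group, allowing for 15% dropout, "will provide adequate power ( $\beta = 0.8" at alpha 0.05, "provided the pooled standard deviation is not greater than the mean difference". Total recruitment is 40.

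The visit schedule measures total testosterone at weeks 0, 12 and 24. The inclusion criteria set an estradiol threshold but no testosterone limit.

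**The concern.** A percentage fall does not fix a sample size by itself; it needs an SD on the same scale. The plan supplies only a condition, that the SD is no larger than the difference. That is the same as assuming a standardised difference of at least 1.0. A reader cannot tell whether this is realistic for a 20% fall, because no mean, SD or pilot source is given. Nor does the plan say whether the SD is that of the change or of the week-24 level.

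This sentence alone justifies recruiting 40. If the condition fails, a true 20% fall could easily be missed, and a non-significant primary result would say less than the power statement implies. Separately, beta conventionally denotes the type II error rate, so the printed symbol contradicts the words beside it.

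**Working it through.** **Inputs from the plan.** Two-sample *t*-test; alpha 0.05; power 0.80 (printed as beta); SD at most equal to the difference, so d = difference/SD = 1.0 at the limit; 1:1 allocation; 15% dropout. Two-sided testing is assumed because it is what reproduces the stated number.

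**Step 1: reproduce the plan's figure.** With d = 1.0, the noncentral *t* calculation gives 16.7, so 17 per arm. Inflating for dropout: 17/(1 − 0.15) = 20 per arm, 40 in total, an exact match. Power with 17 per arm is 80.7%. A one-sided test would need 14 per arm (13.1 rounded up), or 17 after dropout, which does not match. Taking beta = 0.8 literally (power 0.20) would need about 4 per arm, so the symbol is a slip that did not affect the number.

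**Step 2: margin.** The smallest d detectable with 80% power at 17 per arm is 0.99. The design has essentially no slack around d = 1.0.

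**Step 3: link d to the 20% fall, untransformed scale.** Take the difference between arms as 20% of the mean (assuming no change on placebo) and the SD of change as a share *s* of the mean. Then d = 0.20/*s*, and the proviso becomes *s* ≤ 20%.

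| SD of change, % of mean (assumed) | d | Power, 17 per arm |
|---|---|---|
| 20 | 1.00 | 81% |
| 25 | 0.80 | 62% |
| 30 | 0.67 | 47% |
| 40 | 0.50 | 29% |

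**Step 4: the same on the log scale.** A 20% fall is a log difference of −ln(0.8) = 0.223. With residual SD *r* of log testosterone after adjustment for baseline, d = 0.223/*r*.

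| Residual SD of log testosterone (assumed) | d | Power, 17 per arm |
|---|---|---|
| 0.223 | 1.00 | 81% |
| 0.25 | 0.89 | 71% |
| 0.30 | 0.74 | 56% |
| 0.40 | 0.56 | 35% |

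These use the two-sample *t* approximation with 32 degrees of freedom. Losing one for the covariate changes power by about 0.1 percentage point.

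The two tables are not interchangeable: the difference, the scale and the SD all differ. A power statement must use the table for the test that will be run.

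**Step 5: what baseline adjustment gains.** Assume equal variance V at both visits and correlation ρ. The variance of change is 2V(1 − ρ); the ANCOVA residual variance is V(1 − ρ²). The ratio of the second to the first is (1 + ρ)/2: 0.75 at ρ = 0.5 and 0.95 at ρ = 0.9. Adjustment therefore lowers the variance by 25% to 5% over that range, using data already collected.

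**The case against.** The strongest reply is that nothing has been miscalculated. The plan states its proviso openly, 40 follows from it exactly, and the natural reading is that the difference mentioned there is the 20% fall of the preceding sentence. All of that stands. It would be too strong to say that the sample size is wrong, or that the plan promises 80% power unconditionally. What remains is that the condition has no mean, SD or source behind it, so it cannot be checked.

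A reader might also infer that the plan's own testosterone values make the required SD implausible. The background section cites 79 versus 215 ng/dl, and treating those as two kinds of participant would suggest wide spread. The documents do not support this. The values are group levels without SDs, from a non-randomised chart review comparing patients with and without medroxyprogesterone, a different progestogen. They are a treatment contrast, not a baseline distribution. Read as a contrast, (215 − 79)/215 = 63% would, if anything, point to an effect larger than 20%. They cannot settle the SD either way.

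Reading beta = 0.8 as a design with 20% power is likewise untenable: the words say adequate power and the number reproduces at 80%. The correction is editorial.

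Finally, the plan contains no rule that a null result would count as evidence against a 20% fall. That is a risk of interpretation, not something the plan asserts. Baseline adjustment is a modest improvement, not the repair of an invalid test.

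**Conclusion.** The point holds in limited form. Recruitment of 40 is correct for a standardised difference of 1.0 with 17 completers per arm and two-sided alpha 0.05. Adequate power specifically for a 20% fall is conditional and unsupported, because it requires an SD of change no larger than 20% of the mean, or a residual log SD no larger than about 0.22, and the plan justifies neither. An SD of change of 25% instead of 20% of the mean costs 19 percentage points of power (81% to 62%). Every SD beyond the plan's own proviso is an assumption; the documents neither confirm nor contradict the required value. The beta label is wrong but has no effect on the sample size.

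**What to change.** Keep 40 participants and make three changes.

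1. Make the primary analysis an ANCOVA of log week-24 total testosterone on arm and log baseline testosterone. Report the between-arm ratio with its 95% CI.
2. Replace the power sentence with text on that scale, for example: *Seventeen completers per arm give about 81% power (beta about 0.19), two-sided alpha 0.05, for a 20% fall (log difference 0.223) if the baseline-adjusted residual SD of log testosterone is at most 0.22. Power is about 71%, 56% and 35% if it is 0.25, 0.30 or 0.40.* Mark these SDs as assumptions, or give a source if the sponsor has one. Wherever the target is stated, write power = 0.80 (beta = 0.20).
3. State that a non-significant result does not by itself exclude a 20% fall.

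If the *t*-test on untransformed change is kept, use its own figures instead: 81%, 62%, 47% and 29% at an SD of change of 20%, 25%, 30% and 40% of the mean.

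Cost: no extra participants, visits or assays, since baseline and week-24 testosterone are already measured. Changes 2 and 3 are wording. Change 1 alters the primary analysis, so it needs an amendment before unblinding. The stated power will look less favourable.
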